2.1.3.2.2 Exploratory/Tertiary efficacy endpoints

2.1.3.2.2.1 Exacerbations of chronic pulmonary disease tool (EXACT)

The EXACT tool quantifies and measures exacerbations of COPD and assesses the symptomatic manifestations of these COPD exacerbations (see Appendix D). The instrument is a daily diary composed of a total of 14 items representing the following domains:

- Breathlessness (5 items),
- Cough and sputum (2 items),
- Chest symptoms (3 items),
- Difficulty bringing up sputum (1 item),
- Tired or weak (1 item),
- Sleep disturbance (1 item), and
- Scared or worried (1 item).

The EXACT total score assesses COPD exacerbations. The higher the score, the more severe are the symptoms.

The EXACT questionnaire is assessed daily from screening to Visit 16 (Week 52). Baseline EXACT score as well as the post-baseline weekly scores will be calculated as the mean within-patient score over the prior 7 days, with data present for a minimum of 4 of the 7 days. If fewer than 4 days of data are available in the 7-day window, the EXACT score cannot be calculated and will be considered as missing. For the exacerbation analysis, the baseline would be reset during

the study. Additional information related to computing scores and frequency, severity, and duration of events can be found in the user manual (6).

The Evaluating Respiratory Symptoms (E-RS) in COPD (E-RS: COPD) scale is a part of the EXACT tool. It is a derivative instrument used to measure the effect of treatment on the severity of respiratory symptoms in stable COPD. The E-RS utilizes the 11 respiratory symptom items contained in the 14-item EXACT.

The daily COPD RS-Total score is computed by taking the sum of the 11 items comprising the instrument. It has a range of 0 to 40, with higher values indicating more severe respiratory symptoms.

The same summation procedure is used to derive the three daily domain scores:

- COPD RS-Breathlessness (sum of items 7, 8, 9, 10, and 11; score range 0–17)
- COPD RS-Cough and Sputum (sum of items 2, 3, 4; score range 0–11)
- COPD RS-Chest Symptoms (sum of items 1, 5, 6; score range 0–12)

Like for EXACT, the baseline RS score as well as the post-baseline weekly domain and total scores are calculated as the mean within-patient score over the prior 7 days, with data present for a minimum of 4 of the 7 days. If fewer than 4 days of data are available in the 7-day window, the RS scores cannot be calculated and will be considered as missing.

2.1.3.2.2.2 Body-Mass Index, Airflow Obstruction, Dyspnea, and Exercise Capacity Index (BODE Index)

The BODE Index is a composite measure composed of a Performance Outcome Measure, a Patient-Reported Outcome Measure and a Biomarker. The BODE Index is a multidimensional grading system to assess the respiratory and systemic expressions of COPD (7). It comprises 4 domains: 1) Degree of pulmonary impairment (FEV₁ percent predicted); 2) Patient's perception of symptoms (mMRC); and 2 independent domains: the 6 Minute Walking Distance (6MWD) and the Body-Mass Index (BMI). Each domain can be scored independently; the global score ranges from 0 to 10, with a higher score indicating a higher risk of death (see Appendix F for scoring algorithm details)

The BODE index will be assessed at Visit 2 (Week 0) and Visit 16 (Week 52).

2.1.4 Safety endpoints

The safety analysis will be based on the reported adverse events and other safety information, such as clinical laboratory data, vital signs, ECG and physical examination.

Observation period

The observation period will be divided into 4 epochs:

- The **screening** epoch is defined as the time from the signed informed consent date up to the time prior to first administration of the IMP.

- The **treatment** epoch is defined as the time from the first administration of the IMP to the last administration of the IMP + 14 days.
- The **residual treatment** epoch is defined as the time from the last administration of the IMP +15 days to the last administration of the IMP + 98 days.

The treatment-emergent adverse event period will include both **treatment** and **residual treatment** epochs.

- The **posttreatment** epoch is defined as the period of time starting the day after the end of the treatment-emergent adverse event period up to the end of the study (defined as last protocol planned visit or the resolution/stabilization of all serious adverse events and adverse events with pre-specified monitoring).
- The on-study observation period is defined as the time from start of treatment until the end of the study (defined as last protocol planned visit or lost to follow-up or the resolution/stabilization of all serious adverse events and adverse events with pre-specified monitoring).

Safety events adjudication

Adjudication will be performed by experts independent of sponsor for the evaluation of whether deaths, cardiovascular SAEs and respiratory SAEs meet criteria for cardiovascular assessment endpoints. A confirmatory adjudication will occur for AECOPD exacerbations. Adjudicators will adjudicate these events in a consistent and unbiased manner throughout the study.

The goal of the adjudication is to ensure that all events reported by the site are judged uniformly, using pre-specified criteria by a group independent of the Sponsor. Adjudication Committee members will be blinded to treatment allocation. Adjudication Committee members' responsibilities and the process for data review are described in the AC Charter/Manual of Operation.

2.1.4.1 Adverse events variables

Adverse event observation period

- Pretreatment adverse events are adverse events that developed or worsened or became serious during the screening epoch
- Treatment-emergent adverse events are adverse events that developed or worsened or became serious during the treatment-emergent adverse event period
- Posttreatment adverse events are adverse events that developed or worsened or became serious during the posttreatment epoch.

All adverse events (including serious adverse events and adverse events with pre-specified monitoring/of special interests) will be coded to a lower-level term (LLT), preferred term (PT), high-level term (HLT), high-level group term (HLGT), and associated primary system organ class (SOC) using the version of Medical Dictionary for Regulatory Activities (MedDRA) currently in effect at Sanofi at the time of database lock.

The occurrence of adverse events (including serious adverse events and adverse events with prespecified monitoring) will be recorded from the time of signed informed consent until the end of the study.

Cardiovascular assessment

All events submitted for cardiovascular adjudication will be listed and summarized, including the final classification results. A swimmer plot including all events classified as cardiovascular, including cardiovascular death, will also be provided.

Furthermore, events classified as cardiovascular will be evaluated according to the following composite endpoints:

- **Major Cardiovascular Adverse Events (MACE):** cardiovascular death, non-fatal myocardial infarction, or non-fatal stroke
- MACE + hospitalization for unstable angina
- Cardiovascular death: death resulting from myocardial infarction, stroke, pulmonary embolism, heart failure, procedure-related death or other cardiovascular cause.
- Hospitalization: for unstable angina, for atrial fibrillation/flutter, for other symptomatic arrhythmias, for transient ischemic attack.
- Other cardio/cerebrovascular events: non-fatal heart failure, peripheral arterial event, pulmonary embolism, non-acute coronary syndrome/myocardial ischemia, others.

Adverse events of special interest (AESI) and other selected AE groupings will be searched based on the criteria in [Table 2](#).

Table 2 - Criteria for adverse events of special interest and other selected AE groupings

AE Grouping	Criteria
AESI	
Anaphylactic reaction	Anaphylactic reaction algorithmic approach (Introductory Guide for Standardised MedDRA Queries (SMQs) Version 18.1): includes anaphylactic reaction narrow SMQ (20000021) terms and programmatic identification of cases based on occurrence of at least two preferred terms meeting the algorithm criteria occurring within 24 hours of each other. The latter cases identified using the algorithm will undergo blinded medical review taking into account the timing of events relative to each other and to IMP administration for final determination of an anaphylactic reaction or not.
Hypersensitivity (medically reviewed)	SMQ hypersensitivity (20000214) narrow search and [AE corrective treatment/therapy='Y' or Action taken with IMP='Drug withdrawn' or Action taken with IMP='Drug interrupted'] followed by blinded medical review (documented process) for selection of relevant systemic hypersensitivity events
Severe injection site reactions that last longer than 24 hours	HLT = 'Injection site reactions' and with severe status and (AE end date/time - AE start date/time) ≥eg, 24 hours or ongoing
Serious infection	Primary SOC = 'Infections and infestations' and with serious status
Parasitic infection	The Infection Type 'Parasitic' was checked on eCRF page "Infection Event Form"

AE Grouping	Criteria
Infection requires parenteral (intravenous, intramuscular, subcutaneous) antimicrobial therapy	"Have any parenteral treatment (IV, Intramuscular, SC) been given for this event?" was answered Yes on eCRF page "Infection Event Form"
Infection requires oral antimicrobial therapy for longer than 2 weeks	"Did this event require Prolonged Medication (greater than 14 Days)?" was answered Yes on eCRF page "Infection Event Form"
Opportunistic infection	The Infection Type 'Opportunistic' was checked on eCRF page "Infection Event Form"
Pregnancy of a female patient entered in a study as well as pregnancy occurring in a female partner of a male patient entered in a study with IMP/NIMP	"Pregnancy" or "Partner Pregnancy" checked on the Pregnancy eCRF page as reported by the investigator
Symptomatic overdose with IMP	Symptomatic Overdose is answered Yes, with Overdose of IMP answered Yes on AE eCRF.
Symptomatic overdose with NIMP	Symptomatic Overdose is answered Yes, with Overdose of NIMP answered Yes on AE eCRF.
Clinically symptomatic eosinophilia (or eosinophilia associated with clinical symptoms)	HLT = 'Eosinophilic disorders' or PT = 'Eosinophil count increased' followed by blinded medical review for selection of relevant events
Any severe type of conjunctivitis	Based on PTs in (Appendix J) and "Severe" ticked in Adverse Events eCRF page
Any severe type of blepharitis	HLT as "Lid, lash and lacrimal infections, irritations and inflammations" and "Severe" ticked in Adverse Events eCRF page
Keratitis	PT in (keratitis, allergic keratitis, ulcerative keratitis, atopic keratoconjunctivitis, herpes ophthalmic, ophthalmic herpes simplex, corneal infection)
Significant ALT elevation	"ALT increase" was checked and "Is the event an AESI" was answered Yes on AE eCRF as reported by the investigator (ALT $>5 \times$ ULN in participants with baseline ALT $\leq 2 \times$ ULN; OR ALT $>8 \times$ ULN if baseline ALT $>2 \times$ ULN)

Other selected AE grouping

Injection site reactions	HLT = 'Injection site reactions'
Malignancy	Sub-SMQ (20000091)- Malignant or unspecified tumors
Conjunctivitis (narrow)	PT in (Conjunctivitis, Conjunctivitis allergic, Conjunctivitis bacterial, Conjunctivitis viral, Atopic keratoconjunctivitis)
Conjunctivitis (broad)	PT in (Conjunctivitis, Conjunctivitis allergic, Conjunctivitis bacterial, Conjunctivitis viral, Atopic keratoconjunctivitis, Blepharitis, Dry eye, Eye irritation, Eye pruritus, Lacrimation increased, Eye discharge, Foreign body sensation in eyes, Photophobia, Xerophthalmia, Ocular hyperaemia, Conjunctival hyperaemia)
Conjunctivitis (FDA)	PT in (Conjunctivitis, Conjunctivitis allergic, Conjunctivitis bacterial, Conjunctivitis viral, Eye irritation, Eye inflammation, Giant papillary conjunctivitis)
Helminthic infections	HLGT= "Helminthic disorder"
AEs related to COVID-19 illness	SMQ [20000237] – COVID-19 narrow

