8.3.1 Adverse event of special interest

An adverse event of special interest (AESI) is an AE (serious or nonserious) of scientific and medical concern specific to the Sponsor's product or program, for which ongoing monitoring and immediate notification by the Investigator to the Sponsor is required. Such events may require further investigation in order to characterize and understand them. Adverse events of special interest may be added, modified or removed during a study by protocol amendment.

For these AESIs, the Sponsor will be informed immediately (ie, within 24 hours), per SAE notification described in Section 8.3.2, even if not fulfilling a seriousness criterion, using the corresponding pages in the CRF (to be sent) or screens in the e-CRF. If an SAE or any AESI of anaphylactic reactions or systemic allergic reactions that are related to IMP and require treatment, or severe injection site reactions lasting longer than 24 hours, occurs in a patient, blood samples should be collected for determination of functional dupilumab concentration, and ADA assessment at or near the onset and completion of the occurrence of the event, if possible (see Section 8.5.3 for details).

- Clinically symptomatic eosinophilia (or eosinophilia associated with clinical symptoms).
- Anaphylactic reactions or systemic allergic reactions that are related to IMP and require treatment (see Appendix 15, Section 10.15).
- Severe injection site reactions that last longer than 24 hours.
- Any infection meeting at least one of the following criteria:
 - Any serious infection (SAE).
 - Requires parenteral (intravenous, intramuscular, subcutaneous) antimicrobial therapy.
 - Requires oral antimicrobial therapy for longer than 2 weeks.
 - Is a parasitic infection.
 - Is an opportunistic infection (see Appendix 16, Section 10.16).

Note: antimicrobial therapy refers to antibiotic, antiviral, and antifungal agents

- Any severe type of conjunctivitis or blepharitis.
- Keratitis.
- Significant ALT elevation:
 - ALT >5 × the upper limit of normal (ULN) in patients with baseline ALT \leq 2 × ULN, or
 - ALT $> 8 \times ULN$ if baseline ALT $> 2 \times ULN$.
- Pregnancy of a female subject entered in a study as well as pregnancy occurring in a female partner of a male subject entered in a study with IMP/NIMP.

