 - Number (%) of patients with any specific TEAE
 - Number (%) of patients with any specific serious AE (regardless of treatment emergent status)
 - Number (%) of patients with any specific treatment emergent serious AE
 - Number (%) of patients with any specific AE leading to death
 - Number (%) of patients with any specific TEAE leading to permanent study drug discontinuation

- Number (%) of patients with any specific TEAE related to IMP reported by investigator
- Number (%) of patients with any specific TEAE by maximum intensity, corrective treatment, and final outcome
- Number of any specific TEAE adjusted by the exposure duration
- Number of patients with any specific TEAE adjusted by the exposure duration at risk. For each specific TEAE, Kaplan-Meier estimates of cumulative incidence at Week 12, 24, 36 and 52 and K-M plot may be provided to depict the course of onset over time if the number of events is large enough.
- Number (%) of patients with injection site reactions by the related injection.
- Number (%) of patients with different number of injection site reactions.
- In addition, AESIs reported by the investigator in CRF will be summarized separately.

Analysis of pretreatment adverse events

- All pretreatment adverse events by primary SOC and PT, showing the number (%) of patients with at least 1 pretreatment adverse event, sorted by the internationally agreed SOC order and decreasing incidence of PTs within each SOC in the 300 q2w treatment group.
- All serious pretreatment adverse events by primary SOC and PT, showing the number (%) of patients with at least 1 pretreatment adverse event, sorted by the internationally agreed SOC order and decreasing incidence of PTs within each SOC.
- All pretreatment adverse events leading to permanent treatment discontinuation by primary SOC and PT, showing the number (%) of patients, sorted by the internationally agreed SOC order and decreasing incidence of PTs within each SOC.
- All pretreatment adverse events leading to death by primary SOC and PT, showing the number (%) of patients, sorted by the internationally agreed SOC order and decreasing incidence of PTs within each SOC.
- If only a few patients have pretreatment adverse events leading to permanent treatment discontinuation, a listing will be presented instead of the summary table above.

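### Two infection AESIs in SAP Table 2 are derived from eCRF answers that do not ask about antimicrobials (or, for the second, the oral route), so the criteria are broader than Protocol 8.3.1 and than their own row labels

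*SAP*

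**What the plan says.** Protocol 8.3.1 lists, among the infections that are AESIs, one that "Requires parenteral (intravenous, intramuscular, subcutaneous) antimicrobial therapy" and one that "Requires oral antimicrobial therapy for longer than 2 weeks". A note under the list fixes the drug classes: "antimicrobial therapy refers to antibiotic, antiviral, and antifungal agents".

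Protocol 9.4.2 (Table 10) leaves the method of identifying AESIs to the SAP, so SAP 2.1.4.1, Table 2 is the operative rule. Its row label for the first AESI repeats the protocol: "Infection requires parenteral (intravenous, intramuscular, subcutaneous) antimicrobial therapy". The criterion beside that label is a Yes on the Infection Event Form to "Have any parenteral treatment (IV, Intramuscular, SC) been given for this event". The second row also keeps the protocol's label. Its criterion is a Yes to "Did this event require Prolonged Medication (greater than 14 Days" on the same form.

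SAP 2.4.5.1 plans risk differences (Miettinen-Nurminen) and Cox hazard ratios, each with a 95% CI, for the table of AESIs and other AE groupings. It also states: "In addition, AESIs reported by the investigator in CRF will be summarized separately". SAP 2.4.5 describes the safety analysis as essentially descriptive, without systematic testing. SAP 1.6 records no statistical modifications, so a deliberate broadening of the two definitions is not documented.

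**The concern.** In each of the two rows the label and the criterion describe different events. The label promises infections serious enough to need a particular kind of anti-infective treatment. The criterion accepts any parenteral treatment, or any medication lasting more than 14 days, so long as the site attributes it to the infection.

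In this population such treatment is foreseeable. Protocol 2.2 says exacerbations are often triggered by viral or bacterial infection. Protocol 8.1.1.1 names intramuscular, intravenous and oral systemic corticosteroids as exacerbation treatment, and Protocol 6.5 allows them for up to 6 weeks in an acute exacerbation. A respiratory infection reported as an AE and treated with oral antibiotics plus an intravenous corticosteroid could be answered Yes in row 1. One treated with a short oral antibiotic course and a corticosteroid course of more than 14 days could be answered Yes in row 2. Neither need meet the protocol definition.

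What is at stake is the interpretability of two prespecified infection-safety rows for an immunomodulator. A reader of the study report would take the counts to be infections needing parenteral or prolonged oral antimicrobials, and the comparative estimates would be read in that light.

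**Working it through.** **Step 1: definitions side by side.** No figure in the plan bears on this point, so the check begins with the text.

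| Element | Protocol 8.3.1 | SAP Table 2 criterion |
|---|---|---|
| Row 1, route | parenteral | parenteral |
| Row 1, drug class | antibiotic, antiviral or antifungal | not tested |
| Row 2, route | oral | not tested |
| Row 2, drug class | antibiotic, antiviral or antifungal | not tested |
| Row 2, duration | more than 2 weeks | more than 14 days |

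Duration agrees. Drug class is missing from both rows and route from the second, so each criterion is broader than its definition.

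**Step 2: does anything else in Table 2 restore the restriction?** No. Table 2 applies blinded medical review to algorithm-identified anaphylaxis, hypersensitivity and symptomatic eosinophilia. The ALT row requires the investigator to have marked the event as an AESI. The two infection rows have neither condition, nor a concomitant-medication check.

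**Step 3: what could misclassification do?** The documents give no AESI rates and no share of Yes answers that reflect non-antimicrobial treatment. The following is therefore illustration under assumptions:

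- 462 patients per arm (SAP 1.3, all taken as treated).
- True AESI risk p of 3% on placebo and 6% on dupilumab (assumed).
- f is the assumed chance of a false-positive Yes in a patient without a true event.
- Observed risk: q = p + f(1 − p).
- RD = q_D − q_P and RR = q_D / q_P.
- HR under proportional hazards with complete follow-up: ln(1 − q_D) / ln(1 − q_P).
- Approximate 95% CI for RD: RD ± 1.96 × √[q_P(1 − q_P)/462 + q_D(1 − q_D)/462]. This is a Wald interval, used as a stand-in for the planned Miettinen-Nurminen interval.

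Worked example, f = 5% in both arms: q_P = 0.03 + 0.05 × 0.97 = 0.0785; q_D = 0.06 + 0.05 × 0.94 = 0.1070; RD = 2.85 points; RR = 0.1070/0.0785 = 1.36; HR = ln(0.8930)/ln(0.9215) = 1.38.

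| f placebo / f dupilumab | q_P | q_D | RD, points (95% CI) | RR | HR |
|---|---|---|---|---|---|
| 0 / 0 | 3.00% | 6.00% | 3.00 (0.3 to 5.7) | 2.00 | 2.03 |
| 1% / 1% | 3.97% | 6.94% | 2.97 (0.1 to 5.9) | 1.75 | 1.78 |
| 2% / 2% | 4.94% | 7.88% | 2.94 (−0.2 to 6.1) | 1.60 | 1.62 |
| 5% / 5% | 7.85% | 10.70% | 2.85 (−0.9 to 6.6) | 1.36 | 1.38 |
| 5% / 3.75% | 7.85% | 9.53% | 1.68 (−2.0 to 5.3) | 1.21 | 1.22 |
| 2% / 3% | 4.94% | 8.82% | 3.88 (0.6 to 7.1) | 1.79 | 1.82 |

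The fifth scenario assumes that every false positive follows exacerbations at the trial's planning effect, 1.125/1.5 = 0.75, so 5% × 0.75 = 3.75%. The sixth assumes that they follow infections, which in this illustration are more frequent on dupilumab.

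**Step 4: reading the table.** Equal false positives pull the ratio measures toward 1 and widen the RD interval, but hardly move the RD itself. Unequal false positives can lower or raise the RD. Starting from 2% versus 4%, or from 5% versus 8%, gives the same pattern.

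**The case against.** Several points on the other side stand.

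- **The form is not shown.** Only two questions are quoted, under labels that say antimicrobial therapy. Completion instructions may already restrict the answers. Both questions also tie the treatment to the infection, so treatment for something else should not produce a Yes. Miscounting is a possibility, not an established fact.
- **Most steroid-treated exacerbations stay out.** Protocol 8.1.1.1 keeps exacerbations out of AE reporting unless serious, and the 6-week allowance in Protocol 6.5 is for exacerbations. This limits the route but does not close it, because a concurrent pneumonia or bronchitis can still be reported as an infection AE.
- **There are other views of the data.** Serious infection is a separate row, defined by system organ class plus seriousness, and is untouched. Investigator-reported AESIs, reported under the protocol definition, are summarised separately, and each AESI is tabulated by corrective treatment. These are partial checks: they do not alter the Table 2 counts, no rule is given for reconciling two differing counts, and the serious row does not cover non-serious infections.
- **The lack of medical review follows a pattern.** Other rows based on form answers (parasitic, opportunistic, pregnancy, overdose) have none either. That explains the omission, but those rows do not have the label-criterion gap shown above.

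A reader might infer that such infections are in fact being counted and that an excess on dupilumab is thereby hidden. The documents do not support this. They report no imbalance and no false-positive rate. With equal false positives the planned risk difference is almost unchanged, and the direction under unequal ones is unknown. Scenarios with twice as many false positives on placebo go beyond the trial's own planning effect of a 25% reduction.

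**Conclusion.** The mismatch is established from the text: both criteria are broader than Protocol 8.3.1 and than their own labels, and nothing in the SAP corrects the resulting counts. Non-antimicrobial treatment can therefore bring an infection into either row.

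The effect on the comparison cannot be determined from the documents. It could attenuate the hazard ratio and could shift the risk difference in either direction. Under the assumed 3% and 6% true risks, the risk difference ranged from about 1.7 to 3.9 points around a true 3.0, and the hazard ratio from 1.22 to 1.82 against 2.03 without misclassification. Those ranges rest wholly on assumed rates and on the form answers not being restricted to antimicrobials.

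The point concerns descriptive safety reporting only. No efficacy endpoint, alpha level or sample size is affected. It is worth correcting because the definitions should agree and the correction is cheap.

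**What to change.** In SAP Table 2, use the two eCRF answers as a screen and add a confirmation step:

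- **Row 1:** at least one parenteral concomitant medication linked to that infection, in an anti-infective ATC class (antibacterial, antiviral or antifungal).
- **Row 2:** an oral medication in those classes, linked to that infection and taken for more than 14 days.
- **Unclear route or link:** settle by the blinded medical review already used elsewhere in Table 2.
- **Supportive row:** keep the eCRF-only count beside the confirmed count.

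If the Infection Event Form instructions already restrict the answers to antimicrobials, and to oral use for row 2, a sentence in Table 2 saying so is enough.

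The cost is SAP wording, modest programming and a few reviewed cases. Concomitant medications are recorded with reason for use, dates and dose (Protocol 6.5) and summarised by ATC class (SAP 2.4.2). Route is not among the items listed in Protocol 6.5, which is why the review step is needed. No new data collection or protocol amendment is required.
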